4.4. Blinding and Unblinding

Part C of this study is open-label.

5. Analysis Populations

The following analysis sets are defined: Enrolled Set, Solicited Safety Set, Safety set, Full Analysis set (FAS), and Per-Protocol (PP) set.

5.1. Enrolled Set

The Enrolled Set consists of all enrolled participants who received any study injection in Part C. Subjects will be included in the vaccination group corresponding to the vaccination group they assigned.

5.2. Solicited Safety Set

The Solicited Safety Set consists of all participants who are enrolled and received any study injection in Part C, and contribute any solicited AR data, ie, have at least one post-baseline solicited safety assessment. The Solicited Safety Set will be used for the analyses of solicited ARs and subjects will be included in the vaccination group corresponding to the study injection they actually received.

5.3. Safety Set

The Safety Set consists of all enrolled participants who received any study injection in Part C. The Safety Set will be used for analysis of safety except for the solicited ARs. Subjects will be included in the vaccination group corresponding to the vaccination they actually received.

5.4. Full Analysis Set

Full Analysis Set (FAS)

The FAS consists of all enrolled participants who

- a) receive any study vaccination in Part C, and
- b) have baseline (OL-Day 1) immunogenicity data available, and
- c) have at least one post-injection immunogenicity assessment for the analysis endpoint.

Subjects will be included in the vaccination group to which they were assigned.

5.5. Per-Protocol Set

Per-Protocol (PP) Set

The PP Set consists of all FAS subjects who meet all of the following criteria:

- a) Had post-injection immunogenicity assessment at timepoint of primary interest for the immunogenicity analysis
- b) Have had no major protocol deviations that impact immune response during the period corresponding to the immunogenicity analysis objective

The PP Set will serve as the primary population for the analysis of immunogenicity data.

Subjects will be included in the vaccination group to which they were assigned.

6. Statistical Analysis

6.1. General Considerations

The Schedule of Assessments is provided in the protocol Table 12.

Continuous variables will be summarized using the following descriptive summary statistics: the number of subjects (n), mean, standard deviation (SD), median, minimum (min), and maximum (max).

Categorical variables will be summarized using counts and percentages.

Baseline value, unless specified otherwise, is defined as the most recent non-missing measurement (scheduled or unscheduled) collected before the first dose of study injection (OL-Day 1). For immunogenicity tests and nasal swab tests, the baseline is defined as the most recent non-missing measurement (scheduled or unscheduled) collected before or on the date of first dose of study injection (OL-Day 1).

For the summary statistics of all numerical variables unless otherwise specified, the display precision will follow programming standards. Please see [Appendix A](#) for variable display standards.

When count data are presented, the percentage will be suppressed when the count is zero in order to draw attention to the non-zero counts. A row denoted “Missing” will be included in count tabulations where specified on the shells to account for dropouts and missing values. The denominator for all percentages will be the number of subjects in that vaccination group within the analysis set of interest, unless otherwise specified.

Study day relative to the first injection will be calculated as below:

- a) study day prior to the first injection will be calculated as: date of assessment/event – date of the first injection;
- b) study day on or after the date of the first injection will be calculated as: date of assessment/event – date of the first injection + 1.

For calculation regarding antibody levels/titers, antibody values reported as below the LLOQ will be replaced by $0.5 \times \text{LLOQ}$. Values that are greater than the upper limit of quantification (ULOQ) and without actual values reported (eg, ‘>xxx’) will be converted to the ULOQ. Values that are greater than the ULOQ and with actual values reported will not be imputed. Missing results will not be imputed.

This study can be divided into the following **stages**:

- Vaccination stage:
 - For assessments that will be collected throughout the study (eg, unsolicited AE), it consists first injection on OL-Day 1 to 28 days after last injection (ie, the day of last injection and 27 subsequent days).
 - For assessments that will be collected at study visits (eg, vital sign), if a subject receives first injection only, this stage starts at the first injection on OL-Day 1 and continues through OL-Month 1 visit.
- Follow up stage: Begins after the vaccination stage and continue until the earliest date of (study completion, discontinuation from the study, or death).
- OL-Day 1 to End of Study: Begins at the first injection on OL-Day 1 and continues through the earliest date of (study completion, discontinuation from the study, or death).

Unscheduled visits: Unscheduled visit measurements will be included in analysis as follows:

- In scheduled visit windows per specified visit windowing rules.
- In the derivation of baseline/last on-treatment measurements.
- In the derivation of maximum/minimum on-treatment values and maximum/minimum change from baseline values for safety analyses.
- In individual subject data listings as appropriate.

Visit windowing rules: The analysis visit windows for protocol-defined visits are provided in [Appendix B](#).

Incomplete/missing data:

- Imputation rules for missing prior/concomitant medications, non-study vaccinations and procedures are provided in [Appendix C](#).
- Imputation rules for missing AE dates are provided in [Appendix D](#).
- For laboratory assessments, if majority of results are indefinite, imputation of these values will be considered. If the laboratory results are reported as below the LLOQ (eg, <0.1), the numeric values will be imputed by $0.5 \times \text{LLOQ}$ in the summary. If the laboratory results are reported as greater than the ULOQ (eg, >3000), the numeric values will be imputed by ULOQ in the summary.
- Other incomplete/missing data will not be imputed, unless specified otherwise.

The following vaccination **groups** will be used for summary purposes:

- mRNA-1273.351 50 µg
- mRNA-1273/mRNA-1273.351 mixture 50 µg
- mRNA-1273.351 20 µg
- mRNA-1273.351 Total

All analyses will be conducted using SAS Version 9.4 or higher.

6.2. Background Characteristics

6.2.1. Subject Disposition

The number and percentage of subjects in the following categories will be summarized by vaccination group as defined in [Section 6.1](#):

- Enrolled Set
- Solicited Safety Set
- Safety Set
- Full Analysis Set
- PP Set

The percentage will be based on subjects in that vaccination group within the Enrolled Set. For Solicited Safety Set, the percentage will be based on subjects in that vaccination group within the Safety Set.

The number and percentage of subjects in each of the following disposition categories will be summarized by vaccination group based on the Enrolled Set:

- Received study vaccine
- Completed study
- Prematurely discontinued the study and the reason for discontinuation

The denominator for all percentages will be the number of subjects in that vaccination group within the Enrolled Set.

A subject disposition listing will be provided, including informed consent, subjects who completed the study injection schedule, subjects who completed study, subjects who discontinued from study vaccine or who discontinued from participation in the study, with reasons for discontinuation.

A subject who completed OL-Month 6 is considered to have completed Part C of the study.

6.2.2. Demographics

Descriptive statistics will be calculated for the following continuous demographic and baseline characteristics: age at enrollment of the Phase 3 study (years), weight (kg), height (cm), and body mass index (BMI) (kg/m^2). Number and percentage of subjects will be

provided for categorical variables such as gender, race, ethnicity. The summaries will be presented by vaccination group as defined in [Section 6.1](#) based on the Safety Set, PP Set and FAS separately. If the number of participants in the FAS and PP Set differ (defined as the difference divided by the total number of participants in the PP Set) by more than 10%, tables will be provided for both FAS and PP Set, otherwise, only one table will be provided for the PP set.

In addition, subjects with any inclusion and exclusion criteria violation will also be provided in a listing.

6.2.3. Medical History

Medical history will not be re-collected in P201 study. Medical history, including the medical history data and AE data collected in the Phase 3 study, will be coded by system organ class (SOC) and preferred term (PT) using the Medical Dictionary for Regulatory Activities (MedDRA), and be programmatically mapped to the analysis data model (ADaM) datasets in this study for analysis purpose.

The number and percentage of participants with any medical history will be summarized by SOC and PT based on the Safety Set. A participant will be counted only once for multiple events within each SOC and PT. SOC will be displayed in internationally agreed order. PT will be displayed in descending order of frequency of total mRNA-1273.351 and then alphabetically within SOC.

Medical history data will be presented in a listing.

6.2.4. Prior and Concomitant Medications

Medication and non-study vaccination will not be re-collected in P201 study if it has been collected in the Phase 3 study. Prior and concomitant medications and non-study vaccination, including the medication and non-study vaccination data collected in the Phase 3 study and P201 study, will be coded using the World Health Organization (WHO) drug dictionary (WHODD). The data from the Phase 3 study will be programmatically mapped to the ADaM datasets in this study for analysis purpose. The summary of concomitant medications will be based on the Safety Set separately.

The number and percentage of subjects using concomitant medications and non-study vaccination during the 7-day follow-up period (ie, on the day of injection and the 6 subsequent days) and during the 28-day follow-up period after injection (ie, on the day of

injection and the 27 subsequent days) will be summarized by vaccination groups as defined in [Section 6.1](#) as follows:

- Any concomitant medications and non-study vaccination within 7 Days Post Injection
- Any concomitant medications and non-study vaccination within 28 Days Post Injection
- Prophylactic antipyretics or analgesics medication within 28 Days Post Injection
- Antipyretic or analgesic medication within 28 Days Post Injection

A summary table of concomitant medications and non-study vaccination that continued or newly received at or after the first injection through 28 days after the last injection will be provided by PT in descending frequency in the mRNA-1273.351 group with both dose level combined.

Medications taken to prevent pain or fever will be collected on eDiary and summaries will be provided based on the Solicited Safety Set by vaccination group as defined in [Section 6.1](#) for any injection, including within 7 days after injection, beyond 7 days after injection and any time after injection..

Prior, concomitant and post medications and non-study vaccination will be presented in a listing.

Concomitant Procedures will be presented in a listing.

6.2.5. Study Exposure

Study vaccine administration data will be presented in a listing.

6.2.6. Major Protocol Deviations

Major protocol deviations are a subset of protocol deviations that may significantly impact the completeness, accuracy, or reliability of the study data or that may significantly affect a subject's rights, safety, or well-being. Major protocol deviations rules will be developed and finalized before database lock.

The number and percentage of the subjects with each major protocol deviation type will be provided by vaccination group as defined in [Section 6.1](#) based on the Enrolled Set.

Major protocol deviations will be presented in a listing.

6.2.7. COVID-19 Impact

A listing will be provided for COVID-19 impact.

6.3. Safety Analysis

Safety and reactogenicity will be assessed by clinical review of all relevant parameters including solicited ARs (local and systemic), unsolicited AEs, SAEs, MAAEs, AEs leading to withdrawal from study participation, vital signs, and physical examination findings. Solicited ARs and unsolicited AEs will be coded by SOC and PT according to the MedDRA. The Toxicity Grading Scale for Healthy Adult and Adolescent Volunteers Enrolled in Preventative Vaccine Clinical Trials (DHHS 2007) is used in this study for solicited ARs with modifications for rash as presented in Table 4 from protocol.

Rash will be graded as:

- Grade 0 = no rash
- Grade 1 = localized without associated symptoms
- Grade 2 = maculopapular rash covering < 50% body surface area
- Grade 3 = urticarial rash covering > 50% body surface area
- Grade 4 = generalized exfoliative, ulcerative or bullous dermatitis

All safety analyses will be based on the Safety Set, except summaries of solicited ARs which will be based on the Solicited Safety Set. All safety analyses will be provided by vaccination group unless otherwise specified.

6.3.1. Adverse Events

A treatment-emergent AE (TEAE) is defined as any event not present before exposure to study vaccine or any event already present that worsens after exposure to study vaccine. [Note: worsening of a pre-existing condition after vaccination will be reported as a new AE.]

Adverse events will also be evaluated by the investigator for the coexistence of MAAE which is defined as an AE that leads to an unscheduled visit to a healthcare practitioner.

Unsolicited AEs will be coded by PT and SOC using MedDRA and summarized by vaccination group and stage (28 days after any vaccination stage, and OL-Day 1 to End of Study; see [Section 6.1](#) for definitions of vaccination group and stage).

All summary tables (except for the overall summary of AEs) for unsolicited AEs will be presented by SOC and PT for TEAEs with counts of subjects included. SOC will be displayed in internationally agreed order. PT will be displayed in descending order of frequency of total mRNA-1273.351 and then alphabetically within SOC. When summarizing the number and percentage of subjects with an event, subjects with multiple occurrences of the same AE or a continuing AE will be counted once. Subjects will be presented according to the highest severity (the strongest relationship) in the summaries by severity (of related AEs), if subjects reported multiple events under the same SOC and/or PT.

Percentages will be based upon the number of subjects in the Safety Set within each vaccination group.

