3.4.8.7 Eliciting and Documenting Adverse Events

The investigator is responsible for ensuring that all AEs and SAEs are recorded in the eCRF and reported to the Sponsor. Unsolicited AEs will be captured from Day 1 through 28 days after each dose up to Day 57 visit in Part A ([Table 9](#)), up to OL-Day 57 visit in Part B ([Table 11](#) and [Table 12](#)), and up to 28 days after the last injection in Part C ([Table 12](#)). Both MAAEs and SAEs will be captured from blinded (Part A) and open-label (Part B) Day 1 throughout entire study duration (Day 394 for Part A, or 6 months post-last vaccination for Part B and C for all participants), as specified in the respective SOEs ([Table 9](#), [Table 11](#), and [Table 12](#)). Any AEs occurring before receipt of the vaccine will be analyzed separately from TEAEs.

At every study site visit or telephone contact, participants will be asked a standard question to elicit any medically-related changes in their well-being according to the scripts provided. Participants will also be asked if they have been hospitalized, had any accidents, used any new medications, changed concomitant medication regimens (both prescription and over-the-counter medications), or had any non-study vaccinations.

In addition to participant observations, data from clinical laboratory test results, physical examination findings, or other documents relevant to participant safety classified as an AE will be documented on the AE page of the eCRF.

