3.4.8.8 Reporting Adverse Events

The investigator is responsible for reporting all AEs that are observed or reported during the study, regardless of their relationship to vaccine or their clinical significance. If there is any doubt as to whether a clinical observation is an AE, the event should be reported.

All unsolicited AEs reported or observed during the study will be recorded on the AE page of the eCRF. Information to be collected includes cohort, type of event, time of onset, investigator-specified assessment of severity and relationship to vaccine, time of resolution of the event, seriousness, as well as any required treatment or evaluations, and outcome. The unsolicited AEs resulting from concurrent illnesses, reactions to concurrent illnesses, reactions to concurrent medications, or progression of disease states must also be reported. All AEs will be followed until they are resolved or stable or judged by the investigator to be not clinically significant. The Medical Dictionary for Regulatory Activities (MedDRA) will be used to code all unsolicited AEs.

Any medical condition that is present at the time that the participant is screened but does not deteriorate should not be reported as an unsolicited AE. However, if it deteriorates at any time during the study, it should be recorded as an unsolicited AE.

Any AE considered serious by the investigator or that meets SAE criteria ([Section 3.4.8.3](#)) must be reported to the Sponsor immediately (within 24 hours of becoming aware of the SAE). The investigator will assess whether there is a reasonable possibility that the vaccine caused the SAE. The Sponsor will be responsible for notifying the relevant regulatory authorities of any SAE as outlined in the 21 US CFR Parts 312 and 320. The investigator is responsible for notifying the institutional review board (IRB) directly.

If the eCRF is unavailable at the time of the SAE, the following contact information is to be used for SAE reporting:

- SAE Mailbox: [REDACTED]
- SAE Hotline (USA and Canada): [REDACTED]
- SAE Fax line (USA and Canada): [REDACTED]

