Consists of all periods that begin 28 days after the last injection in Part A (ie, the day of last injection in Part A + 28 days, regardless of number of injections received) and continue until the earliest date of first injection in Part B, and all periods that begin 28 days after the last injection in Part B (ie, the day of last injection in Part B + 28 days, regardless of number of injections received) and continue until the earliest date of (study completion, discontinuation from the study, or death).

- Day 1 to End of Study: Begins at the first injection on Day 1 and continues through the earliest date of (study completion, discontinuation from the study, or death).
- 28 days after any vaccination stage: This stage starts at the day of each vaccination and continue through the earliest date of (the day of each vaccination and 27 subsequent days, next vaccination (if applicable)).

Unscheduled visits: Unscheduled visit measurements will be included in analysis as follows:

- In scheduled visit windows per specified visit windowing rules.
- In the derivation of baseline/last on-treatment measurements.
- In the derivation of maximum/minimum on-treatment values and maximum/minimum change from baseline values for safety analyses.
- In individual subject data listings as appropriate.

Visit windowing rules: The analysis visit windows for protocol-defined visits are provided in [Appendix B](#).

Incomplete/missing data:

- Imputation rules for missing prior/concomitant medications, non-study vaccinations and procedures are provided in [Appendix C](#).
- Imputation rules for missing AE dates are provided in [Appendix D](#).
- For laboratory assessments, if majority of results are indefinite, imputation of these values will be considered. If the laboratory results are reported as below the LLOQ (eg, <0.1), the numeric values will be imputed by $0.5 \times \text{LLOQ}$ in the summary. If the laboratory results are reported as greater than the ULOQ (eg, >3000), the numeric values will be imputed by ULOQ in the summary.

- Other incomplete/missing data will not be imputed, unless specified otherwise.

The following vaccination **groups** will be used for summary purposes:

- Part A, Blinded Phase:
 - mRNA-1273 50 µg
 - mRNA-1273 100 µg
 - mRNA-1273 Total
 - Placebo
- Part B, Open-Label Phase:
 - mRNA-1273 50 µg - Booster
 - mRNA-1273 100 µg - Booster
 - mRNA-1273 - Booster Total
 - Placebo - mRNA-1273

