6.3.1. Adverse Events

A treatment-emergent AE (TEAE) is defined as any event not present before exposure to study vaccine or any event already present that worsens after exposure to study vaccine. [Note: worsening of a pre-existing condition after vaccination will be reported as a new AE.]

Adverse events will also be evaluated by the investigator for the coexistence of MAAE which is defined as an AE that leads to an unscheduled visit to a healthcare practitioner.

Unsolicited AEs will be coded by PT and SOC using MedDRA and summarized by age cohort, vaccination group, and stage (28 days after any vaccination stage for Part A and Part B separately, and Day1 to End of Study; see [Section 6.1](#) for definitions of vaccination group and stage).

All summary tables (except for the overall summary of AEs) for unsolicited AEs will be presented by SOC and PT for TEAEs with counts of subjects included. SOC will be displayed in internationally agreed order. PT will be displayed in descending order of frequency of total mRNA-1273 and then alphabetically within SOC. When summarizing the number and percentage of subjects with an event, subjects with multiple occurrences of the same AE or a continuing AE will be counted once. Subjects will be presented

according to the highest severity (the strongest relationship) in the summaries by severity (of related AEs), if subjects reported multiple events under the same SOC and/or PT.

Percentages will be based upon the number of subjects in the Safety Set within each vaccination group.

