6.3.1.2. TEAEs by System Organ Class and Preferred Term

The following summary tables of TEAEs will be provided by SOC and PT using frequency counts and percentages (ie, number and percentage of subjects with an event):

- All unsolicited TEAEs
- All unsolicited TEAEs that are treatment-related
- All serious TEAEs
- All serious TEAEs that are treatment-related

- All unsolicited TEAEs leading to discontinuation from participation in the study
- All unsolicited Severe TEAEs
- All unsolicited Severe TEAEs that are treatment-related
- All unsolicited TEAEs that are medically-attended

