6.3.1.1. Incidence of Adverse Events

An overall summary of unsolicited TEAEs including the number and percentage of subjects who experience the following will be presented:

- Any unsolicited TEAEs
- Any serious TEAEs
- Any unsolicited TEAEs that are medically-attended
- Any unsolicited TEAEs leading to discontinuation from participation in the study
- Any unsolicited Severe TEAEs
- Any unsolicited TEAEs that are fatal

The table will also include number and percentage of subjects with unsolicited TEAEs that are treatment-related in each of the above categories.

In addition, separate listings containing individual subject adverse event data for unsolicited AEs, unsolicited TEAEs leading to discontinuation from participation in the study, serious AEs, and unsolicited MAAEs will be provided separately.

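### Both SAPs run the 'any', 'related' and 'severe' unsolicited TEAE tables to the end of the study, although parts of the protocol stop routine capture of non-serious, non-attended, non-discontinuation events about 28 days after each injection and other parts do not

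*SAP*

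**What the plan says.** **Analysis.** Section 6.3.1 of the Parts A and B SAP summarises unsolicited AEs by "vaccination group, and stage (28 days after any vaccination stage for Part A and Part B separately, and Day1 to End of Study". Section 6.3.1 of the Part C SAP uses "vaccination group and stage (28 days after any vaccination stage, and OL-Day 1 to End of Study". In the Parts A and B SAP (6.1) the longer stage is a single span covering both parts: "Day 1 to End of Study: Begins at the first injection on Day 1 and continues through the earliest date of (study completion", discontinuation or death). Sections 6.3.1.1 to 6.3.1.4 of each SAP tie no table to one stage. Their lists include "Any unsolicited Severe TEAEs" and "All unsolicited Severe TEAEs that are treatment-related" alongside all and all treatment-related unsolicited TEAEs. Percentages use the number of participants in the Safety Set.

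**Collection, narrow reading.** Protocol 3.4.7 and the safety endpoints in 4.3 limit unsolicited AEs to 28 days after each injection. Section 3.4.8.7 captures them to Day 57 in Part A, to OL-Day 57 in Part B, and "up to 28 days after the last injection in Part C". The rows for recording unsolicited AEs stop at Day 57 in Table 9 and OL-Day 57 in Table 11. In Table 12 the OL-Day 57 and OL-Day 64 marks carry footnote 12, which concerns the additional booster. MAAEs, SAEs and AEs leading to discontinuation continue to the end of each part. Section 3.1.1 describes the two-weekly Part A contacts after Day 57 as collecting those types, with no mention of general AEs.

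**Collection, wide reading.** Section 3.4.2 lists AEs among the things the later eDiary is meant to pick up. The call script in 3.4.3 and the call footnotes to Tables 9, 11 and 12 also ask about AEs. Section 3.4.8.8 sets no time limit: "All unsolicited AEs reported or observed during the study will be recorded on the AE page of the eCRF".

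**The concern.** A percentage labelled Day 1 (or OL-Day 1) to End of Study will be read as the share of participants with an event over that whole period. On the narrow reading, the 'any' and 'related' rows combine full collection in the first weeks with collection of only attended, serious or discontinuation events afterwards. The percentage is then too low for its label, and event dates would appear to bunch after vaccination because of how they were collected. If sites follow different parts of the protocol, late events will also depend on site practice.

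The protocol's own unsolicited-AE endpoint is not at stake, since the 28-day stage reports it. What is at stake is the meaning of the end-of-study tables still to be produced for Part B and Part C.

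**Working it through.** The documents state no figure for this coverage, so there is none to reproduce.

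**Inputs.** Window: 28 days per injection (protocol 3.4.7). Last study day: 394 in Part A (3.1.1), OL-181 for Part B boosters and Part C (Table 12), OL-209 for two doses in Part B (Table 11).

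**Coverage by part.** Share = (28 × injections) / last study day. It applies only to events that are non-serious, non-attended and did not lead to discontinuation; for the other types, coverage is 100%.

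| Group | Calculation | Share |
|---|---|---|
| Part A, two doses, followed to Day 394 | 56/394 | 14.2% |
| Part A, one dose | 28/394 | 7.1% |
| Part B booster, 28-day rule | 28/181 | 15.5% |
| Part B booster, if capture runs to OL-Day 57 | 57/181 | 31.5% |
| Part B crossover, two doses | 56/209 | 26.8% |
| Part C, single booster | 28/181 | 15.5% |
| Part C, with a second booster | 56/181 | 30.9% |

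The two Part B booster rows reflect an ambiguity in 3.4.8.7, which gives both 28 days after each dose and OL-Day 57. Table 12's conditional mark favours the 28-day reading.

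**Coverage on the joined Parts A and B stage.** The duration of Part A varies because it ends when Part B starts; 209 to 394 days is assumed. Share = (Part A windows + Part B windows) / (Part A days + Part B days).

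- Booster: (56 + 28)/(209 + 181) = 84/390 = 21.5%, down to 84/575 = 14.6%.
- Placebo crossover: (56 + 56)/(209 + 209) = 112/418 = 26.8%, down to 112/603 = 18.6%.
- No Part B dose: 56/390 = 14.4%, down to 56/575 = 9.7%.

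**Number of windows in Part B.** This is a separate display matter, and it affects the 28-day stage too. A booster column has one window and a crossover column two. If a fraction p of participants has an event in each window, independently, the expected percentages are p and 1 − (1 − p)². With p assumed to be 20% these are 20% and 36%; with 10%, 10% and 19%; with 30%, 30% and 51%. On the joined stage the counts are three and four windows: 1 − 0.8³ = 49% and 1 − 0.8⁴ = 59% (27% and 34% at 10%; 66% and 76% at 30%).

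**The case against.** The strongest reply is that the protocol does look for AEs later. The eDiary and calls alternate about every two weeks after Day 57 or OL-Day 57, several passages name AEs separately from MAAEs and SAEs, and 3.4.8.8 has no cut-off. This stands, so a reader should not infer that such events are certainly absent after 28 days. It does not settle the matter the other way. The questionnaire items in 3.4.2 cover health changes, exposure, symptoms, MAAEs and SAEs, and follow-up is for events relevant to the study period. The schedule rows still stop.

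A reader might also infer that the end-of-study safety rates as a whole rest on 14–27% of follow-up. They do not. That range describes one class of event, is calculated by part, and omits the single-dose Part A and second-booster Part C cases.

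The severe rows are less exposed. Protocol 3.4.8.9 defines Grade 3 as requiring medical intervention, so most late severe events should also be MAAEs.

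Nor does the 20% against 36% example show the end-of-study problem. It reflects one window against two, and no formal comparison of those columns is planned. It supports a display by injection and nothing more.

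Finally, the Parts A and B SAP (Section 1) says the Part A reports are final, so a change to Part A tables is no longer practical. That stands.

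**Conclusion.** The point holds in a limited form. The SAPs apply a whole-study stage to 'any', 'related' and, less importantly, 'severe' unsolicited TEAEs, while the protocol gives conflicting rules on whether non-serious, non-attended, non-discontinuation events are recorded after about 28 days. On the 28-day rule the shares in the table apply to that class. If 3.4.8.8 is the operative rule and all sites followed it, the mixing largely disappears, but 3.4.8.7 and the schedules would then be wrong.

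The joined-stage figure of about 10–27% depends on the assumed Part A duration. The SAE, MAAE and discontinuation tables are sound on either reading. This is worth correcting before the remaining outputs are run; it does not threaten a protocol endpoint.

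**What to change.** 1. Reconcile protocol 3.4.2, 3.4.3, 3.4.8.7, 3.4.8.8 and the schedule rows and footnotes, and state in both SAPs which capture rule applied.
2. For the remaining Part B and Part C analyses (6.3.1 to 6.3.1.4), limit the end-of-study tables to SAEs, MAAEs, AEs leading to discontinuation and fatal events. Show severe events there only within those types.
3. Give 'any', 'related' and 'severe' unsolicited TEAEs for the 28-day post-injection stage. Split it into injection 1 and injection 2 for Part B crossovers, so that like windows sit side by side.
4. Define the 28-day stage in section 6.1 of the Part C SAP; 6.3.1 refers to it there, but no stage of that name is defined.
5. Keep later non-attended events in the unsolicited AE listings already planned.
6. For Part A, add a footnote on the collection window wherever the tables are reused.

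The changes need no new data, only SAP wording and some table changes. The downside is that late non-attended events reported spontaneously would appear in a listing and not in a percentage.
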